ALT	Alanine aminotransferase
ANOVA	Analysis of variance
APFS	Accessorized pre-filled syringe device
AST	Aspartate aminotransferase
AUC	Area under the concentration-time curve
AUC _{inf}	Area under the concentration-time curve from time zero extrapolated to infinity
AUC _{last}	Area under the concentration-time curve from time zero to the last observed time point
BLQ	Below the lower limit of quantification
BMI	Body Mass Index
CI	Confidence interval
CL/F	Apparent extravascular clearance
C _{max}	Maximum observed concentration
CRF	Case Report Form
CRP	C-reactive protein
CSP	Clinical Study Protocol
CV	Coefficient of variation
DRM	Data review meeting
ECG	Electrocardiogram
FSH	Follicle-stimulating hormone
GGT	Gamma glutamyl transpeptidase
Hb	Hemoglobin
IMP	Investigational Medical Product

ABBREVIATION AND ACRONYM LIST

Statistical Analysis Plan

Abbreviation / Acronym	Definition / Expansion
LLOQ	Lower limit of quantification
LS	Least square
MedDRA	Medical Dictionary for Regulatory Activities
NA	Not applicable
NC	Not calculated
NCA	Non-compartmental analysis
ND	Not determined
NR	No result
PDS	protocol deviation specification
РК	Pharmacokinetic
Q1	25 th percentile
Q3	75 th percentile
QCD	Quantitative Clinical Development
RBC	Red blood cell
SAE	Serious adverse event
SAP	Statistical Analysis Plan
SC	Subcutaneous
SD	Standard deviation
SOC	System Organ Class
t½	Terminal half-life
TEAE	Treatment-emergent adverse event
TLFs	Tables, Listings and Figures
T _{max}	Time when the maximum concentration is observed
TOST	Two one-sided tests
TSH	Thyroid-stimulating hormone
V _z /F	Apparent volume of distribution based on the terminal phase
WBC	White blood cell
$\lambda_{z,}$ Lamda Z	First order rate constant associated with the terminal (log-linear) elimination phase
%AUCextra	Percentage of AUC obtained by extrapolation

AMENDMENT HISTORY

Date	Version change	Brief description of change
26 June 2017	Final 1.0 to Draft 6.0	• Remove Physical Examination appendix based on protocol amendment 1. Abnormal results at baseline will be included as part of Medical History and abnormal results post baseline will be included as AEs. As a result, physical examination will not be listed by body system for each subject and each time point.
		• PK vendor change from MedImmune to PXL QCD
		• Add summary tables for both PK concentration and PK parameters by injection site and weight category

STATISTICAL ANALYSIS PLAN

The Statistical Analysis Plan (SAP) details the statistical methodology to be used in analyzing study data and outlines the statistical programming specifications for the Tables, Listings and Figures (TLFs). It describes the variables and populations, anticipated data transformations and manipulations and other details of the analyses not provided in the Clinical Study Protocol (CSP).

The analyses described are based on the final 1.0 CSP, dated, 19/Oct/2016 and the protocol amendment 1.0, dated 07/Jul/2017. The statistical analysis plan (SAP) will be prepared prior to first subject enter treatment period and any subsequent amendments will be documented, with final amendments completed prior to database lock. Any deviations from the SAP after database lock, reasons for such deviations and all alternative or additional statistical analyses that may be performed, will be described in a SAP Addendum. The SAP describes the statistical analysis as it is foreseen when the study is being planned.

1. STUDY OBJECTIVES

1.1 Primary Objective

• To compare the pharmacokinetic (PK) exposure following single subcutaneous (SC) administration of benralizumab by using Accessorized pre-filled syringe (APFS) or Autoinjector (AI) devices

1.2 Secondary Objectives

- To evaluate the PK of benralizumab administered to various anatomical injection sites and in subjects with different body weight ranges
- To evaluate the safety and tolerability of benralizumab
- To evaluate the immunogenicity of benralizumab

2. STUDY DESIGN

This study will be a randomized, open-label, parallel group Phase 1 study designed to compare benralizumab PK exposure in healthy subjects following single SC administration of fixed 30 mg dose of benralizumab by using APFS and AI. Eligible subjects will be healthy subjects aged 18 to 55 years, with a body weight of 55.0 to 100.0 kg and a body mass index (BMI) of 18 to 29.9 kg/m² inclusive. A total of 180 subjects will be randomized. Randomization will be stratified by weight group (55.0 to 69.9 kg, 70.0 to 84.9 kg and 85.0 to 100.0 kg), and within each of the 3 weight groups, subjects will be randomized 1:1:1:1:1:1

AstraZeneca AB D3250C00030 Final 2.0 04/Aug/2017

Statistical Analysis Plan

one of the 6 combinations of treatment (APFS or AI) with injection site (upper arm, abdomen or thigh), shown in Table 1. This study will be performed at 2 study centers.

Table 1Design of a Pharmacokinetic Comparability Study in Healthy Subjects
for Benralizumab Accessorized Pre-Filled Syringe and Autoinjector
Devices

Number of Subjects		APFS			AI			
		Upper arm	Abdomen	Thigh	Upper arm	Abdomen	Thigh	Total
	55.0 to 69.9 kg	10	10	10	10	10	10	60
Body Weight	70.0 to 84.9 kg	10	10	10	10	10	10	60
	85.0 to 100.0 kg	10	10	10	10	10	10	60
Total			90			90		180

AI: Autoinjector; APFS: Accessorized pre-filled syringe device

The study will comprise:

- A screening period, maximum of 28 days,
- On treatment period during which subjects will be resident from the day before dosing (Day -1) until 2 hours after dosing on Day 1. The subjects will then return to the center for ambulant visits on Days 2, 4, 5, 6, 8, 15, 29 and 43, and
- An End-of-Treatment visit on Day 57 (Week 8).

After enrolment, eligible subjects will enter a screening period of maximally 28 days. Subjects will return to the unit on Day -1 (1 day before dosing) to reassess their eligibility. Subjects who meet eligibility criteria will be randomized on Day 1 to receive a single dose of 30 mg benralizumab by either APFS or AI device. The study will be completed after the End-of-Treatment visit on Day 57 (Week 8).

A schedule of assessments is given in Section 7.2, Table 2 of the CSP.

3. STUDY POPULATION

This study will be conducted in male and female subjects. The study may not necessarily be balanced regarding gender. The study was not formally powered to detect differences between genders for the primary endpoint. It is not planned to perform sub-analyses on gender.

Statistical Analysis Plan

Detailed lists of inclusion and exclusion criteria are shown in Sections 7.5.1 Inclusion Criteria and 7.5.2 Exclusion Criteria of the CSP.

4. STATISTICAL BASIS FOR SAMPLE SIZE

While this study is not a formal bioequivalence study, a total of 162 subjects (81 subjects per group) are required for this study to achieve with 80% power and a 90% two-sided confidence interval (CI) for geometric mean ratios of area under the concentration-time curve (AUC) and maximum observed concentration (C_{max}) being within a limit of 0.8 to 1.25 inclusive. The calculation is based on two one-sided tests (TOST) at 5% alpha level under an assumption of maximum 50% coefficient of variation (CV) PK variability for primary endpoints of benralizumab AUC and C_{max} . Assuming 10% dropout rate, approximately 180 subjects will be enrolled to provide adequate numbers of subjects to assess the primary and secondary objectives of the study.

5. **RANDOMIZATION**

A total of 180 subjects will be randomized. Subjects will be stratified by body weight category (55.0-69.9 kg/70.0-84.9 kg/85.0-100.0 kg). Within each of the 3 weight groups, subjects will be randomized 1:1:1:1:11 to one of the 6 combinations of treatment (APFS or AI) with injection site (upper arm, abdomen or thigh). As a result, 10 subjects will be allocated to each of the 18 randomization combinations for 2 device groups (Table 1). Randomization lists will be prepared for each study site separately. Randomization numbers will be assigned to subjects sequentially within each weight category at each site. To keep the balance, each site must ensure they randomize subjects in complete blocks.

Once a randomization number has been allocated to a subject, it should not be assigned to another subject.

Day -1 body weight assessment will be used to categorize the body weight groups.

6. STATISTICAL ANALYSIS CONVENTIONS

6.1 Analysis Variables

6.1.1 Demographic and Background Variables

The following demographic and anthropometric information will be recorded at Screening unless otherwise stated:

• Date of informed consent

Statistical Analysis Plan

- Medical history (including start and stop dates [or ongoing if applicable], medical history term)
- Age (years)
- Sex
- Ethnic origin (Hispanic or Latino, Not Hispanic or Latino)
- Race (American Indian or Alaska Native, Asian, Native Hawaiian or Other Pacific Islander, Black or African American, White or Other)
- Height (cm) at Screening
- Body weight (kg) at Screening and Day -1
- Body mass index BMI calculated as [weight/height²] (kg/m²), obtained at Screening

Age and BMI will obtained from the Case Report Form (CRF) and not re-calculated outside the study database.

6.1.2 **Prior and concomitant medication**

The following information will be given:

- Medication or therapy, indication
- Start and end date and time, ongoing, prior
- Dose frequency, route, units

6.1.3 Drug administration

Benralizumab administration dates and times will be recorded for each subject. The location of administration (arm, thigh or abdominal wall), the device type (APFS or AI), dose and dose unit will also be recorded.

6.1.4 Pharmacokinetic Variables

Blood samples for determination of serum benralizumab concentration will be collected at the following time points: Day 1 Pre-dose, Days 2, 4, 5, 6, 8, 15, 29, 43 and 57.

Where possible, the following PK parameters will be assessed for benralizumab on serum concentrations. Additional PK parameters may be determined and reported as appropriate.

Parameter	Definition
AUC _{inf}	Area under the concentration-time curve from time zero extrapolated to infinity
AUC _{last}	Area under the concentration-time curve from time zero to the last observed time
	point
CL/F	Apparent extravascular clearance
C _{max}	Maximum observed concentration
t _{1/2}	Terminal half-life
T _{max}	Time when the maximum concentration is observed
V _z /F	Apparent volume of distribution based on the terminal phase
λ_z	First order rate constant associated with the terminal (log-linear) elimination phase
%AUC _{evtra}	Percentage of AUC obtained by extrapolation

 Table 2
 Pharmacokinetic Parameters after Single Dose Administration

6.1.4.1 Pharmacokinetic Parameter Calculation Methods

The PK analyses of the serum concentration data for benralizumab will be performed by PXL Quantitative Clinical Development (QCD).

Non-compartmental PK analysis (NCA) will be performed using Phoenix WinNonlin (version 6.3, or higher, Certara, Princeton, New Jersey), in accordance with PXL SOPs.

PK analysis will, where possible, be carried out using actual sampling times recorded in the raw data. If actual times are missing, nominal times will be used. A non-compartmental approach consistent with the route of administration will be used for parameter estimation.

PK parameters will be estimated according to the following guidelines:

- C_{max} and T_{max} will be obtained directly from the concentration-time data.
- AUC_{last} will be estimated using the linear/log trapezoidal method.
- AUC_{inf} will be estimated as the sum of corresponding AUC_{last} and $C_{last}/\lambda z$ values:

$$AUC_{inf} = AUC_{last} + \frac{C_{last}}{\lambda_z}$$

- CL/F will be calculated as: $CL/F = \frac{\text{Dose}}{\text{AUC}_{inf}}$
- V_z/F will be calculated as: $Vz/F = \frac{CL/F}{\lambda_z}$

• Terminal half-life (t_{1/2}) will be calculated as: $t_{1/2} = \frac{\ln(2)}{\lambda_z}$, where λ_z is the first-order terminal rate constant estimated via linear regression of the terminal log-linear decay phase.

6.1.5 Immunogenicity Variables

Anti-drug Antibody (ADA) sampling will be collected at the following time points: Day 1 pre-dose, Day 29 and 57. A sample is defined as positive if the reported titer is 50 or above.

For each subject, the following responses variables will be evaluated:

- ADA positive at any visit (at baseline and/or post-baseline)
- ADA positive at both baseline and post-baseline
- ADA positive at post-baseline only
- ADA positive at baseline only

At the study level, a subject's ADA status will be defined as being ADA positive if a positive ADA result is available at any time (including baseline or any post-baseline measurements); otherwise a subject's ADA status will be defined as ADA negative.

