6.3.3 Missing Data

Missing dates and times in the AE data will be handled as described in Section 6.3.11.1. Concentrations that are BLQ in the PK data will be handled as described in Section 6.3.9.2.

There will be no imputations of other missing data. All subjects will be included into the safety analysis set as far as the data permit.

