6.3.10 Immunogenicity Analysis

ADA results will be listed by treatment (device), subjects study ADA status with positive study status first and then subjects with negative study status, subject identifier, and visit including ADA titer and eosinophil count [Appendix 16.2.6.3].

ADA responses observed during the study, as specified in Section 6.1.5, will be summarized by treatment (device) and overall [Table 14.2.4.2]. ADA positive and negative status will be summarized by visit, treatment (device) and overall [Table 14.2.4.1].

Statistical Analysis Plan

The hypersensitivity reported on treatment period will be presented by preferred term for ADA status [Table 14.2.4.3].

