6.3.11.1 Adverse Events

All AEs will be coded using MedDRA vocabulary, and will be listed by treatment (device) for each subject. A Treatment-emergent adverse event (TEAE) is defined as an AE with onset (start date/time) after dosing.

AEs will be assigned to the treatment period or pre-treatment as follows:

- Pre-treatment: All AEs with start date/time prior to dosing.
- Treatment period: AEs with start date/time at the time of or after dosing until the final visit.

The following listings will be included:

- MedDRA coding, including MedDRA lowest level term; PT and SOC [Appendix 16.2.7.1].
- Onset and resolution, including pre-treatment AE, PT, verbatim term, date of onset and resolution and time from IMP [Appendix 16.2.7.2].
- Relationship and causality, including PT, verbatim term, severity, action taken, outcome, causality, SAE and withdrawn [Appendix 16.2.7.3].
- Table of Key Information listing AEs leading to death [Table 14.3.2.1].
- Table of Key Information listing SAE [Table 14.3.2.2].
- Table of Key Information listing AEs that led to discontinuation from study (DAE) [Table 14.3.2.3].
- Table of Key Information listing for AEs associated with device malfunction [Table 14.3.2.4].
- Table of Key Information listing for AEs associated with injection site reactions [Table 14.3.2.5].

All key information listings for AEs will display the baseline eosinophil count and the subject ADA status.

Tabulation of subject counts

A summary (n and percentage) of subjects with at least one AE per category, including AEs with outcome death or discontinuation and SAEs will be presented by treatment (device) and overall [Table 14.3.1.1].

Adverse events subject based, will be summarized by treatment (device) and overall, by SOC and PT. The overall summary will additionally be by pre-treatment and treatment period respectively [Tables 14.3.1.2.1 - 14.3.1.2.2].

Causality of AE will be summarized by treatment (device) and overall, by PT [Table 14.3.1.3]. Maximum intensity of AE will be summarized by treatment (device) and overall by PT [Table 14.3.1.4].

Adverse events associated with injection site reactions will be summarized by subject counts and percentages, by treatment (device), administration site and PT [Table 14.3.1.5].

Tabulation by episode count

A summary of the number of episodes by categories, including AEs with outcome death or discontinuation and SAEs will be presented by treatment (device) and total [Table 14.3.1.6].

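### Study-level ADA status labels subjects with no post-dose result negative unless positive before dosing, and pools pre-dose-only positives with those who turned positive after dosing

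*SAP*

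**What the plan says.** **Sampling and sample-level rule (SAP 6.1.5).** "Anti-drug Antibody (ADA) sampling will be collected at the following time points: Day 1 pre-dose, Day 29 and 57". Positivity is judged per sample: any titer of at least 50 counts.

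**Study-level rule (SAP 6.1.5).** A subject is ADA positive if "a positive ADA result is available at any time (including baseline or any post-baseline measurements"; failing that, the subject's "ADA status will be defined as ADA negative". No post-baseline result is required for the negative label, and there is no category for missing or unevaluable subjects.

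**Response categories (SAP 6.1.5).** Four are listed: positive at any visit, "ADA positive at both baseline and post-baseline", positive post-baseline only, and positive at baseline only. SAP 6.3.10 summarizes them by device and overall in Table 14.2.4.2.

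**Use with safety data.** SAP 6.3.10: "The hypersensitivity reported on treatment period will be presented by preferred term for ADA status" (Table 14.2.4.3, safety analysis set). SAP 6.3.11.1: "All key information listings for AEs will display the baseline eosinophil count and the subject ADA status".

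**Missing data (SAP 6.3.3).** After AE dates and BLQ concentrations are dealt with, "There will be no imputations of other missing data". Nothing there is specific to ADA.

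**Purpose.** Immunogenicity is a secondary objective. Protocol 11.11 plans to evaluate a possible link between ADA and safety and to look at hypersensitivity by ADA status. Protocol 5.5 describes hypersensitivity as a theoretical risk of developing ADA.

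**The concern.** The label used alongside safety data merges groups that mean different things.

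- **Unknown counted as negative.** The first post-dose ADA sample is on Day 29. Under Protocol 7.5.3, a subject with unacceptable symptoms is withdrawn. A baseline-negative subject withdrawn for a reaction before Day 29, with no later sample, would appear in Table 14.2.4.3 as an ADA-negative hypersensitivity case, although post-dose status was never measured. The missing result may thus be related to the very event being tabulated.
- **Pre-existing counted with developed.** Exclusion criterion 25 (Protocol 7.5.2) bars prior benralizumab, so a pre-dose positive cannot have been induced by the drug. It nevertheless carries the same label as a positive that first appears on Day 29 or Day 57.

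At stake is how the one ADA-by-safety table and the AE key listings are read.

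**Working it through.** The plan gives no figure to reproduce here, so the check applies the SAP 6.1.5 rule to each possible pattern.

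| Pre-dose result | Day 29/57 results | Study-level status under the rule | Timing category in 6.1.5 |
|---|---|---|---|
| Negative | At least one positive | Positive | Post-baseline only |
| Positive | At least one positive | Positive | Both |
| Positive | Sampled, all negative | Positive | Baseline only |
| Positive | None available | Positive | Not stated; baseline only by default |
| Negative | Sampled, all negative | Negative | None |
| Negative | None available | Negative | None |
| Missing | None available | Negative | None |

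The last two rows receive the same label as subjects sampled and found negative. Rows 1 and 3 share the positive label.

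**Does another output separate these groups?**
- Table 14.2.4.2 separates row 1 from row 3, but is by device and not crossed with safety.
- Table 14.2.4.1 gives status by visit, not by subject.
- Table 14.2.4.3 is on the safety set, which requires only dosing (SAP 6.2.2), so the last two rows are in it.
- Appendix 16.2.6.3 lists titers by subject and visit, so a reader could reclassify by hand.
- No table or response category isolates subjects without a post-dose result.

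**Illustration on assumed rates.** The documents supply N = 180 and an overall 10% dropout assumption (180 × 0.10 = 18). They give no ADA rates and no dropout timing. Assume:
- b = 1–5% positive pre-dose with no later positive;
- p = 2–10% positive post-dose among those sampled;
- d = 2–10% with no post-dose sample. The upper end would need all planned dropout to fall before Day 29.

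Share of the positive group that is pre-dose only = N·b / [N·b + N(1 − d)p]:
- low (b 1%, p 10%, d 2%): 1.8 / (1.8 + 17.64) = 9%;
- high (b 5%, p 2%, d 10%): 9 / (9 + 3.24) = 74%.

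Share of the negative group never sampled post-dose = N·d(1 − b) / (N − all positives):
- low (b 1%, p 2%, d 2%): 3.564 / (180 − 1.8 − 3.528) = 2%;
- high (b 1%, p 10%, d 10%): 17.82 / (180 − 1.8 − 16.2) = 11%.

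Expected post-dose positives hidden among those never sampled = N·d(1 − b)p, if they would turn positive at the same rate as those sampled:
- low (b 5%, p 2%, d 2%): 180 × 0.02 × 0.95 × 0.02 = 0.07;
- high (b 1%, p 10%, d 10%): 180 × 0.10 × 0.99 × 0.10 = 1.78.

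These ranges follow from the chosen inputs. They show that the size is undetermined, not that it is large.

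**The case against.** The strongest reply is that any-time positivity is a stated and internally consistent prevalence label. The protocol speaks of ADA, not treatment-emergent ADA, in its analysis section. Antibody present at dosing could plausibly matter for a reaction after a single dose, and it is the only ADA measured before Day 29. That stands: pooling is an error only if the table is meant to address ADA that develops after dosing, which is how Protocol 5.5 frames the risk. It does not rescue the negative label for subjects with no post-dose result.

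Stronger readings that the documents do not support:

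- **That the rule misstates ADA incidence.** Table 14.2.4.2 reports post-baseline-only and baseline-only responses separately. The SAP states no denominator for it, so a diluted incidence cannot be shown.
- **That every subject without post-dose samples is called negative.** One who was positive at baseline is called positive.
- **That several ADA-by-safety analyses are biased.** There is one such table. The key-information listings are subject-level and estimate no association.
- **That the rule breaches the no-imputation sentence.** It classifies subjects; it fills in no missing titer.
- **That the primary comparison is compromised.** SAP 6.3.9.1 allows concentration data tied to positive ADA status to be excluded, as decided at the data review meeting. Only if study-level status were used there would pre-dose-only positives risk losing primary data.

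The SAP also does not say outright which status Table 14.2.4.3 uses. The shells, which were not available for this review, may say so.

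**Conclusion.** The point holds in a limited form. Under SAP 6.1.5, a dosed subject with a negative or missing baseline and no post-dose result is labelled ADA negative, and pre-dose-only positives are pooled with post-dose positives. That this label enters Table 14.2.4.3 and the key listings rests on its being the only subject-level positive/negative status defined. The first problem is a misclassification on any reading of the aim; the second depends on wanting ADA that develops after dosing.

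The effect cannot be sized from the documents. It concerns a descriptive analysis under a secondary objective and changes neither the sample size nor the power. It is worth correcting before database lock because the correction is cheap and the missing results may be linked to early reactions.

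**What to change.** 1. **SAP 6.1.5.** Require at least one post-baseline result for ADA-negative status. Add a 'not evaluable' category for dosed subjects without one.
2. **Table 14.2.4.3 and the AE key-information listings.** Show status as post-baseline only, both baseline and post-baseline, baseline only, negative, and not evaluable. The first three are already defined.
3. **Table 14.2.4.2.** Base percentages that depend on post-baseline status on subjects with a baseline and at least one post-baseline result, and state that denominator. A baseline-positive subject with no later result then leaves the baseline-only count. Any-time positivity can stay as a prevalence row.
4. **Optional.** Split the 'both' category by titer rise, with a threshold fixed from the assay before database lock. The documents give no such threshold, and items 1 to 3 do not need one.
5. **SAP 6.3.9.1.** State whether the optional PK exclusions use sample-level or study-level status.

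The cost is one extra derived variable and small cell counts in one descriptive table. Titers are already collected, so no new samples are needed.
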